This is a randomized, repeated measures, matched group study. There will be two groups of participants, 8 participants per group, 35 participants total from time of initial enrollment in this study. Group one (G1) will receive bilateral custom braces and a standardized home walking/exercise program. Group two will receive the standardized walking/exercise program without any brace or AFO. Subjects will be randomized upon enrollment in the study. At the time of consent, random drawing from concealed envelopes with red, blue or green chips will be done to determine group assignment. Subjects will be recruited through the Clinical Center for Movement Disorders at UT Southwestern Medical Center where patients with PD receive routine evaluation and follow-up. Subjects will be followed for 6 months during this study and outcome measures will be collected 3 times over the course of the study. Subjects will be seen every 3 months for the duration of the study for testing as well as for other visits as noted in the table below. Participants will not need to have insurance benefits for initial physical therapy evaluation and for ankle braces. All subsequent visits to the Crowley gait lab for assessments and brace adjustment will be provided at no cost to the participants.

Outcome measures

Testing Procedures:

6-Minute Walk Test: Each subject will be asked to walk at a self-selected velocity on level surfaces for 6 minutes. They will be allowed to use assistive devices if necessary.

Computerized Gait Analysis: Each subject will be asked to walk on a 12-16 foot long vinyl pad placed on the floor. The mat will record and analyze temporal and spatial gait parameters.

Observational Gait analysis: Gait will be evaluated using the Observational Gait Analysis system during over ground walking. A sample of the gait will be videotaped for detailed analysis.

Three-Dimensional gait analysis: Prior to testing, subjects will be outfitted with small retro-reflective markers secured to anatomical locations with easily removable tape. Once markers have been positioned properly, the subject will then be asked to walk up and down a level 15-foot walkway. Four walking trials will be recorded for averaging purposes.

Four Square Step Test: Balance while stepping in different directions will be assessed using this test. Skills such as stepping over an obstacle and stepping backwards are included in the test.

Falls data: Patients will be asked to fill out a fall log at home.

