Short Orientation-Memory-Concentration Test of Cognitive Impairment: Gross cognitive function will be tested using this brief questionnaire.

Daily Activity: Steps per day recorded from a pedometer the patients will wear for the week prior to each testing visit. Daily walking (steps/day) will be recorded throughout the study.

PDQ-39: The PDQ-39 is the most widely used Parkinson's Disease specific measure of health status. It contains thirty nine questions, covering eight aspects of quality of life. The instrument was developed on the basis of interviews with people diagnosed with the disease. It has been widely validated, and translated into over fifty languages.

4. Study Procedures: -

Screening, consent and randomization	Confirm medical diagnosis and medical history, assess sensation and range of motion. Consent process. Appointment made for casting.	60 minutes
Baseline Testing (T1)	Initial outcome measures completed with no	120 minutes

	orthoses and first set of orthoses.	
Visit 1 - 4 Month 1	Gait training session. Instruct in home walking program.	45 minutes
Visit 5 – Month 2		
Testing 2 (T2) – Month 3	All outcome measures completed.	120 minutes
Visit 6 and 7- Month 4 & 5	Gait training session.	45 minutes
Testing 3 (T3) – Month 6	All outcome measure completed	120 minutes

The gait training home program is outlined as follows:

- One to two bouts of focused walking per day. Regardless of the number of walking bouts, the goal is 30 minutes total per day.
- Increase the bouts by 2-5 minutes as tolerated working up to 30 minutes total
- Each subject will receive individualized tape walking protocol based on GAITRite data
- Each subject will receive standard instructions for a home exercise program and will receive handouts

5. Sub-Study Procedures:

There are no sub-studies.

6. Criteria for Inclusion of Subjects:

1. Confirmed diagnosis of Parkinson's Disease according to the UK brain bank criteria.⁵
2. Age between 30 and 85.
3. Measurable decrement in gait velocity (between 35 and 15 percent below age-predicted norms for self-selected walking velocity) as measured by the 6 MWT
4. Hoehn and Yahr stage 2-3.
5. Less than 10 full heel raises in single limb stance bilaterally.

7. Criteria for Exclusion of Subjects:

1. Body mass index greater than 40.
2. Passive dorsiflexion range of motion less than approximately neutral (90 degrees)
3. Any other uncontrolled health condition for which gait training is contraindicated
4. Self-report of > 1 fall/month

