5. A score of 11 or less on the Short Orientation-Memory-Concentration Test of Cognitive Impairment

8. Sources of Research Material:

Some data will be extracted from the medical record to provide needed information prior to treatment. This includes: prior medical history, confirmation of Parkinson's diagnosis, medication history and use. The dependent assessments include: The outcome measure for the study include: 1. GAITRite System for temporal and spatial parameters, 2. Kinematics, 3. 6-Minute Walk Test (gait endurance), 4. Four Square Step Test, 5. Video tape of over ground gait analysis, 6. PDQ-39 (Parkinson's Disease Questionnaire 8), 7. Falls data; 8. Daily activity (pedometer).

9. Recruitment Methods and Consenting Process:

Subjects will be recruited through the Clinical Center for Movement Disorders at UT Southwestern Medical Center where patients with PD receive routine evaluation and follow-up. Each participant will be scheduled to attend an initial meeting at the School of Health Professions Gait Disorders Clinic. The research project will be explained by [name] using the Subject Consent Form as a guide and participants will be randomized to the groups following consent. If they are candidates. This meeting will take approximately 90 minutes. A second visit will be scheduled for the initial assessments and this will take approximately 120 minutes. The original consent and HIPAA Authorization will be maintained in the research file, and the participant will receive a copy of each.

10. Potential Risks:

There is minimal risk involved in participating in this study. There may be minor skin irritation as the result of the new brace(s) as well as minor skin irritation from the surface electrodes used in the EMG testing. There may be minimal fatigue associated with the walking and testing sessions.

11. Subject Safety and Data Monitoring:

The participant's identity will be kept in a separate locked file cabinet in the David M. Crowley Research and Rehabilitation Lab. The subjects will be closely monitored during treatment and testing.

12. Procedures to Maintain Confidentiality:

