Each participant will be assigned a unique identification number once it has been determined that the person meets the inclusion criteria and has signed the consent form and HIPPA authorization form. The unique number will be used to identify all data sets for the individual participant. De-identified information obtained during this study will be released to requesting agencies only with a written release of information from the participant. The results of this research may appear in scientific publications but the participants' names will not be used. All data will be maintained in a research folder in a locked cabinet in the David M. Crowley Research and Rehabilitation Laboratory. The UT Southwestern Institutional Review Board is responsible for assuring that participants' rights are respected. Members of the staff may review records for audit purposes. That review will take place at The Department of Physical Therapy.

13. Potential Benefits:

It is anticipated that the application of this orthosis will result in an immediate improvement in gait parameters (temporal and spatial) as well as long term improvements in activity and gait tolerance as well as balance and strength.

14. Biostatistics:

The proposed design thus consists of two treatment groups ("between" effect) with 8 patients (subjects)/group studied over 3 test sessions ("within" effect). At each data point, nine classes of measures are to be obtained, e.g., the 6-minute walk test, computerized gait analysis, etc. Some of these classes may yield more than one measure. We propose four groups of analyses.

Intent to treat analysis.

Not all patients who initially consent and are randomized may complete the study. We plan to compare (a) those that finish with those who do not finish to see if they differ with respect to any of the dependent variables and (b) the proportions of those who do not finish to see if they are equally divided among the groups. The former will be compared by means of *t*-tests or its nonparametric

counterpart, the Mann-Whitney U, depending upon how well normality assumptions are met. The latter will be compared by means of chi-square or Fisher exact test depending upon sample size. Preliminary psychometric analyses.

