We feel it important to evaluate the relations among the various classes of dependent variables by intercorrelating them to infer their structure, e.g., how many dimensions do they span and are any sufficiently redundant so they can be combined. This involves standard item analysis and exploratory factor analysis. Similar analyses will be performed on the scores obtained from the inclusion measures and other demographics, e.g., can the Hoehn and Yahr scores be combined with other measures to obtain a composite impairment measures that can serve as a better covariate.

Analysis of observed measures

If all patients who complete the study do so without missing any of the test sessions, ordinary repeated measures analysis of variance (ANOVA) will be used to evaluate the main effect of groups, the main effect of testing sessions, and their interaction. Planned comparisons will be employed comparing (a) groups G1 and G2 with each other. This involves comparing what in effect are two control conditions with each other and their average against the active treatment condition. This will be done as a series of univariate tests.

Next, we will examine the effects of covariates such as age of onset and impairment as inferred through the Hoehn and Yahr scale and other measures, again in a univariate manner.

We will then perform a multivariate analysis of variance (MANOVA) to test the null hypotheses that differences on the three effects of interest (groups, testing session, and their interaction) are all nonsignificant across the set of dependent variables.

It is quite likely that there will be missing data from patients who fail to attend one or more testing sessions. We will deal with this problem in two ways. One is to attempt to impute the missing data (see next subsection). The other is to use a mixed model (random regression) which does not require all data to be present, e.g. can analyze the testing effect using whatever data are present. This allows for the same univariate tests to be conducted, but makes multivariate testing extremely difficult to impossible with the data as obtained.

Analysis of imputed measures

Assuming there will be missing data, we will attempt to impute the missing data and perform the analyses as listed in the previous section, including the MANOVA, on these imputed data.

References

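### Falls come from a home log with no described pre-T1 interval, yet Section 14 analyses them as a three-session measure; they need a rate model with log time as offset

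*Combined protocol and SAP*

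**What the plan says.** Section 3 (Outcome measures) says of this outcome only: "Falls data: Patients will be asked to fill out a fall log at home". Section 8 lists it among the outcome measures: "7. Falls data; 8. Daily activity (pedometer". The other home-recorded measure, the pedometer, has a defined window of one week before each testing visit. Falls have none.

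Section 14 describes "8 patients (subjects)/group studied over 3 test sessions" and states: "At each data point, nine classes of measures are to be obtained". The procedures listed in Section 3 number exactly nine, and falls is one of them. Ordinary repeated-measures ANOVA (group, session, interaction) applies if completers miss no session. Then: "We will then perform a multivariate analysis of variance (MANOVA"), across the set of dependent variables. Missing sessions are handled by a mixed model and, separately, by imputation followed by the same analyses, including the MANOVA. Section 14 also compares finishers with non-finishers on the dependent variables, by t-test or Mann-Whitney.

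The only falls information described before T1 is an exclusion criterion in Section 7: "Self-report of > 1 fall/month". No count model, fall rate or person-time appears anywhere.

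**The concern.** A gait test at T1, T2 and T3 is the same measurement taken three times. A fall log is different: it accumulates events over the time it is kept. T2 and T3 each close a 3-month interval, and the documents describe no comparable interval closing at T1. A session factor for falls may therefore compare log lengths instead of fall frequency, and a multivariate test that needs all three sessions may have no T1 value to use.

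The second difficulty concerns subjects who leave. Someone who stops between T2 and T3 has a log covering part of an interval and no T3 visit. A model indexed by session has no cell for that information. The finisher versus non-finisher comparison would set logs of different length side by side.

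At stake are a false statement that falls changed over time, an unusable or largely imputed multivariate test, and the loss of logged falls from early leavers.

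**Working it through.** The plan gives no fall rate, dropout rate, alpha or power, so there is no figure of its own to reproduce. All rates below are assumptions, and alpha is taken as 0.05 two-sided.

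**1. T1 absent.** A complete-data MANOVA needs T1, T2 and T3 on every variable. If no log precedes T1, 0 of the 16 subjects (2 × 8) have a complete falls vector. With imputation, every T1 falls value is imputed, with no observed T1 value from which to build the imputation model. A mixed model can still estimate group and group-by-session effects over T2 and T3, but it cannot estimate the T1 cell.

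**2. T1 shorter than T2 and T3, falls scored as counts.** Expected count = rate × window. At 0.5 falls per month:
- T1 over 1 month: 0.5 × 1 = 0.5
- T2 and T3 over 3 months each: 0.5 × 3 = 1.5

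The expected count triples with no change in the fall rate. Null simulation: 8 per group, 3 sessions, gamma-Poisson counts (gamma shape 1), constant rate, no treatment effect, F-tests on 2 and (16 − 2) × 2 = 28 degrees of freedom, 3,000 runs per setting. The rates stay within the entry ceiling of 1 fall per month.

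| T1 window (months) | Session rejection at 0.25 / 0.5 / 1 fall per month |
|---|---|
| 0 (T1 fixed at zero) | 84.4% / 98.7% / 99.9% |
| 0.5 | 60.9% / 89.4% / 98.8% |
| 1 | 36.2% / 68.1% / 92.7% |
| 3 (equal windows) | 4.3% / 4.4% / 4.8% |

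The group-by-session test rejected 3.6% to 4.9% of the time in every setting.

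**3. Finishers versus non-finishers.** If non-finishers leave at month 3 with the same fall rate, their expected logged falls are 3/6 = half those of finishers. Assume 35 randomised, 19 leaving (35 − 16), 0.3 to 0.6 falls per month and frailty variance 0.7. The t-test or Mann-Whitney on logged totals then rejects about 31% to 46% of the time with no true difference. This applies only if totals are compared; the plan does not say how falls are scored.

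**4. What a rate model gains.** Same assumptions, but with leavers at random times and a true rate ratio of 0.5:

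| Analysis | Power |
|---|---|
| Completers only | 12% to 22% |
| Available full intervals | 20% to 29% |
| Overdispersed Poisson with offset, all 35 | 29% to 40% |

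Type I error of the offset model was about 5% to 6.6%.

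**5. Source of the gain.** In a separate run at rates 0.3 / 0.6, within completers the t-test had 14% / 21% power and the offset model 13% / 20%. In all 35, a t-test on simple rates had 29% / 39% and the offset model 29% / 42%. The gain comes mostly from using everyone randomised and their partial logs, not from the count distribution.

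**The case against.** The strongest reply is that the documents are silent here, not wrong. T1 is a separate visit after consent (Section 9), so a log kept before T1, or a recall value at T1, is possible. Nothing says falls are scored as raw counts. This stands, and the T1 results above are therefore conditional. It does not rescue the plan: a log started at consent covers an unstated interval, and recall is a different instrument from a log.

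A reader might infer that the treatment comparison itself is invalid. It is not on this ground: with equal fall rates the group-by-session test kept its size under every T1 window.

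A reader might also infer that the plan reads dropout as fewer falls. The documents do not support that. Missing sessions go to a mixed model or imputation, and non-completion is compared between groups. A subject who leaves exactly at month 3 has a full T1-T2 interval and a missing T3, which is no truncated count. Bias between arms would need partial logs entered as totals together with unequal dropout, and the plan prescribes neither.

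Finally, falls appear in none of the three hypotheses and are not among the risks in Section 10. That limits the consequence, but falls remain a listed outcome with an assigned analysis that does not fit them.

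**Conclusion.** The point holds as a correction to a secondary outcome. Section 14 assigns falls an analysis that needs a comparable value at T1, and no such value is described. Without a T1 value, the MANOVA loses its subjects or relies on wholly imputed T1 falls. With a shorter T1 log scored as counts, the session main effect is spurious: 36% to 93% false rejection with a 1-month window, and more with a shorter one. The plan also cannot use partly completed logs, and its finisher comparison would mix logs of different length.

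These sizes rest on assumed fall rates, between-subject variation, T1 windows and dropout. Reading 35 enrolled against 8 per group as 19 leaving is also an assumption, since Section 3 says only "8 participants per group, 35 participants total from time of initial enrollment in this study". The power gain depends on the same assumptions, and even the better analysis stays below 50% power.

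**What to change.** - Remove falls from the three-session ANOVA, mixed model, MANOVA and factor analysis.
- State that the analysed log runs from T1 to last contact, define the unit as the number of falls, and record the days each log was kept.
- Compare arms in all randomised subjects with a Poisson model with estimated overdispersion (or negative binomial), group as the effect and log(days logged) as offset. Report falls per person-month by arm.
- A subject with no logged days cannot enter the model; report the number of such subjects by arm.
- In the finisher versus non-finisher comparison, use falls per month logged.
- Add screening fall frequency as a covariate only if the number is actually recorded; the documents show only an exclusion threshold.

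Cost: SAP wording, one extra model and a days-logged field. Falls leave the joint multivariate test, and type I error may be slightly above 5% at this sample size.

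### Three eligibility tests are not scheduled before the randomisation draw, and no rule covers a patient found ineligible after it

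*Combined protocol and SAP*

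**What the plan says.** All references are to the combined protocol and SAP.

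- **Timing of the draw (section 3, Concise Summary of Project):** "At the time of consent, random drawing from concealed envelopes with red, blue or green chips will be done to determine group assignment".
- **Content of that visit (section 4, first row of the visit table):** "Confirm medical diagnosis and medical history, assess sensation and range of motion", then consent and an appointment for casting. The row is titled as screening, consent and randomisation and is given 60 minutes.
- **Criteria that need a test (sections 6 and 7):** "Measurable decrement in gait velocity (between 35 and 15 percent below age-predicted norms for self-selected walking velocity) as measured by the 6 MWT"; "Less than 10 full heel raises in single limb stance bilaterally"; and, as an exclusion, "A score of 11 or less on the Short Orientation-Memory-Concentration Test of Cognitive Impairment".
- **Where those tests appear:** section 3 describes the 6MWT and the cognitive test among the outcome measures. Section 4 first schedules outcome measures at T1, and section 9 places the initial assessments at a second visit. No visit mentions heel raises.
- **Signs that eligibility comes first:** section 9 says "participants will be randomized to the groups following consent. If they are candidates". Section 12 assigns the study number "once it has been determined that the person meets the inclusion criteria and has signed the consent form".
- **Planned numbers (section 3):** "8 participants per group, 35 participants total from time of initial enrollment in this study".

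**The concern.** Randomisation protects the comparison only if the decision to admit a patient is made before the arm is known. Here the schedule shows the draw at one visit and the first listed 6MWT at the next. The documents describe no blinding. The chip reveals the arm, casting is booked at the same visit as the draw, and the T1 row already refers to a first set of orthoses, so a braced-group patient may have been cast, or even fitted, before the velocity criterion is checked.

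The velocity criterion is the most exposed of the three. It depends on effort, it has both an upper and a lower limit, and the same test is an outcome. The other two criteria are one-sided. If borderline patients were judged at T1, the decision to keep or exclude them could differ by arm, and no later analysis would restore the comparison. Section 14 would also count patients who were never eligible among the non-finishers, because it has no separate category for them.

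**Working it through.** **1. The order of procedures.** There is no planned figure to reproduce, so the check sets the sections side by side.

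| Criterion | In the screening row? | First place the schedule puts it |
|---|---|---|
| Passive ankle range of motion (section 7, item 2) | Yes | Screening visit |
| 6MWT velocity (section 6, item 3) | No | T1, as an outcome |
| Heel raises (section 6, item 5) | No | No visit |
| Cognitive score (section 7, item 5) | No | T1, as an outcome |

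The placement of the cognitive test at T1 can be cross-checked. Section 14 counts nine classes of measure at each data point. Section 3 describes nine, and the cognitive test is one of them. Section 8 lists eight outcome measures and leaves it out, but the count in section 14 matches section 3.

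**2. Sections 9 and 12.** Section 9 makes randomisation depend on candidacy, in a sentence fragment that names no test. Section 12 ties the study number, not the envelope, to the inclusion criteria. Both show intent; neither places the three tests before the draw.

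**3. A rule for late ineligibility.** Section 14 compares finishers with non-finishers among those randomised. No section says whether a patient found ineligible after the draw stays, leaves, or is analysed.

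**4. How easily could it arise?** The documents give no share of drawn patients who would fail a later test, so a share f is assumed. The chance of at least one in n is 1 − (1 − f)^n, and the expected number is n × f.

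| Assumed f | Expected of 16 | P(at least one of 16) | Expected of 35 | P(at least one of 35) |
|---|---|---|---|---|
| 5% | 0.8 | 1 − 0.95^16 = 56% | 1.75 | 83% |
| 10% | 1.6 | 1 − 0.90^16 = 81% | 3.5 | 97% |
| 20% | 3.2 | 1 − 0.80^16 = 97% | 7 | >99.9% |

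With 8 per group, one patient is 1/8 = 12.5% of an arm.

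**5. Illustration of a differential decision.** Assume that the velocity decrement among drawn patients is normal with mean m and SD s. Assume also that one arm keeps patients up to 40% below norm while the other holds to 35%. The mean of a normal truncated to (a, b) is m + s[φ(α) − φ(β)]/[Φ(β) − Φ(α)], with α = (a − m)/s and β = (b − m)/s. The shift is the mean on (15, 40) minus the mean on (15, 35).

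| m, s | Mean on (15, 35) | Mean on (15, 40) | Shift, points | SD on (15, 35) | Shift / SD |
|---|---|---|---|---|---|
| 25, 10 | 25.00 | 26.45 | 1.45 | 5.40 | 0.27 |
| 20, 10 | 23.56 | 24.46 | 0.9 | 5.29 | 0.17 |
| 25, 15 | 25.00 | 26.97 | 1.97 | 5.60 | 0.35 |
| 20, 15 | 24.30 | 25.93 | 1.63 | 5.58 | 0.29 |

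The range is 0.9 to 2.0 points of norm, or 0.17 to 0.35 of the SD inside the window. Neither the distributions nor the 5-point tolerance comes from the documents.

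**The case against.** The strongest reply is that the row is a summary, not a full list. It also omits age, body mass index, Hoehn and Yahr stage and fall history, and nobody would infer that those wait until T1. It does list range of motion, itself an exclusion criterion, so eligibility checking is expected at that visit. Section 3 mentions an initial physical therapy evaluation, patients come from a clinic that evaluates them routinely, and the first meeting is at a gait disorders clinic. The tests could be done at any of these. Sections 9 and 12 show that the intent is to randomise only eligible patients.

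Much of this stands, and it rules out two stronger readings:

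- A reader might infer that ineligible patients will be randomised and then kept or removed by staff who know the arm. The documents do not say so. No section describes removal after the draw or names who would decide.
- A reader might take the gap between 35 enrolled and 2 × 8 = 16 in the design (19 of 35, 54%) as the expected loss from late ineligibility. The documents give no reason for the gap, so it cannot be used that way.

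What the reply does not do is supply a procedure. Age, body mass index, stage and fall history can be had from the chart or by asking. The three tests must be performed, and two of them are scheduled elsewhere. Section 8 names only history, diagnosis and medication as data drawn from the medical record. A site following the table as written could draw first and measure later.

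**Conclusion.** The concern holds as a gap and a conflict, not as a description of what will happen. The schedule does not place the 6MWT velocity, heel-raise or cognitive criteria before the draw. It sits uneasily with sections 9 and 12, and no rule covers a patient found ineligible afterwards. Harm follows only if the tests do wait until T1; selection with the arm known then becomes possible.

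The documents give no basis for a firm size. The chances in step 4 rest on an assumed ineligible share, and the shift in step 5 is illustrative only. The case for action does not depend on either: groups of 8 are sensitive to one or two such decisions, and the damage cannot be repaired once patients are enrolled.

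**What to change.** 1. In the section 4 table, add the unbraced 6MWT, the heel-raise count for each limb and the cognitive test to the screening row, after consent and before the draw.
2. In section 3, replace the timing of the draw with a statement that the envelope is opened only after every inclusion and exclusion criterion has been documented as satisfied. Complete the broken sentence in section 9 to match.
3. Count patients who fail before the draw as screen failures. In section 14, state that everyone drawn stays in the assigned group for the intent-to-treat analysis, including anyone later found ineligible.
4. Reconcile the length of the first visit: 60 minutes in section 4, about 90 in section 9.

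The cost is an edit to the wording and the table, a longer first visit, and some consented patients becoming screen failures. All three tests are already required by the criteria, so no new assessment is added.

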This study has three hypotheses. 1) subjects who are fit with carbon fiber orthoses will demonstrate better spatial and temporal gait parameters compared to controls; 2) subjects who are fit with carbon fiber orthoses will demonstrate improvements in gait kinematics during gait as compared to controls, and 3) as a result of the improvements in their mobility, subjects fit with carbon fiber orthoses will have an overall improvement in their quality of life compared to controls.

2. Background:

Parkinson's disease results in a variety of functional impairments including weakness, gait dysfunction and postural changes. Exercise has been a key tool in the treatment of such limitations, although there is not robust evidence supporting any specific type of intervention in the management of PD.² There is some evidence that exercise in general can be beneficial regarding quality of life, strengthening, balance and gait speed but optimum dosing and exact content of the ideal intervention has not been identified.³ Gait dysfunction is one of the most disabling effects of PD yet clear direction on how to treat this problem is lacking. While there is evidence of brain disturbances leading to gait problems⁴ it is also acknowledged that weakness and sensory loss are significant contributors to gait dysfunction in PD.¹

Orthotic management of gait disturbance in diagnoses such as stroke and brain injury is common as such devices have the potential to address weakness as well as sensory impairment. However, the potential role of bracing in PD has not been explored in the literature. This study is designed to

evaluate the effectiveness of bracing on some of the common manifestations of gait dysfunction in PD.

3. Concise Summary of Project:

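### The three-session ANOVA names no deciding effect for any hypothesis, its group main effect averages in the T1 session, and the brace condition of the values analysed is not stated

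*Combined protocol and SAP*

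**What the plan says.** Section 14 (Biostatistics, analysis of observed measures) plans a repeated measures ANOVA "to evaluate the main effect of groups, the main effect of testing sessions, and their interaction". The MANOVA that follows treats the same three effects as all being of interest. The only focused contrast reads "Planned comparisons will be employed comparing (a) groups G1 and G2 with each other". The next sentence explains it as "comparing what in effect are two control conditions with each other and their average against the active treatment condition". Section 3 describes two groups, braced and unbraced, and section 14 gives 8 patients per group over three sessions.

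The hypotheses in section 1 are comparisons with controls, for example "subjects who are fit with carbon fiber orthoses will demonstrate better spatial and temporal gait parameters compared to controls". None names a session, a change from T1 or a model effect.

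The T1 row of the table in section 4 is broken across a page. It runs "Initial outcome measures completed with no" and then "orthoses and first set of orthoses". The T2 row says "All outcome measures completed", the T3 row says much the same, and neither states whether braces are worn. Section 13 anticipates that gait parameters improve as soon as the orthosis is applied, with longer-term gains in other areas.

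The covariates listed in section 14 are age of onset, Hoehn and Yahr impairment and unspecified other measures, possibly combined into a composite. An outcome's own T1 value is not among them.

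**The concern.** An ANOVA on three sessions that include a pre-treatment one offers two different answers to whether G1 did better than G2. The group main effect compares the average over all sessions, T1 included. The interaction compares the pattern over sessions. They differ in what they estimate and in power, and the plan does not say which one settles a hypothesis. The planned comparison should close that gap, but it has no session or scale, and its explanation cannot be carried out with two groups.

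For the performance tests (gait mat, kinematics, 6-minute walk, Four Square Step Test) there is a second gap. If G1 has both an unbraced and a braced T1 value, the plan does not say which one enters the model. A braced T1 may already contain the effect that Hypotheses 1 and 2 concern.

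**Working it through.** **Inputs from the documents.** Two groups, 8 per group, three sessions (section 14). No SD, effect size, correlation, alpha or power is given, so there is no stated figure to reproduce.

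**Assumptions, for illustration only.** SD 1; equal correlation r = 0.5, 0.7 or 0.9 between sessions; two-sided 0.05; true effect 1 SD. Effects at (T1, T2, T3) are written v.

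**What the main effect estimates.** With unbraced T1 and a constant later effect d, v = (0, d, d), and the main effect estimates (0 + d + d)/3 = 2d/3.

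**Formulas** (n = 8 per arm)
- Main effect: variance of a three-session mean (1 + 2r)/3; noncentrality mean(v)/√(2 × variance/n); 14 df.
- Interaction: F on 2 and 28 df, λ = (n/2) × Σ(v − mean v)²/(1 − r).
- One-df contrast, T2/T3 mean minus T1: variance 1.5(1 − r); 14 df with its own error, or 28 df pooled, which needs sphericity.
- T2/T3 mean adjusted for T1: residual variance (1 + r)/2 − r², times 1 + 1/12 for chance T1 imbalance; 13 df.

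**Example, r = 0.5, v = (0, 1, 1).**
- Main effect: variance 2/3; noncentrality 0.667/√(2 × 0.667/8) = 1.63; power 33.1%.
- Interaction: λ = 4 × 0.667/0.5 = 5.33; power 48.6%.
- Adjusted mean: variance 0.5 × 13/12 = 0.542; noncentrality 1/√(2 × 0.542/8) = 2.72; power 71.0%.

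| Power (%), unbraced T1, v = (0, 1, 1) | r = 0.5 | r = 0.7 | r = 0.9 |
|---|---|---|---|
| Group main effect | 33.1 | 28.5 | 25.1 |
| Interaction, 2 df | 48.6 | 71.6 | 99.5 |
| One-df contrast, own 14-df error | 57.5 | 79.2 | 99.8 |
| One-df contrast, pooled 28 df | 60.6 | 82.1 | 99.9 |
| T2/T3 mean adjusted for T1 | 71.0 | 84.1 | 99.7 |

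Against the 14-df contrast the covariate adds 71.0 − 57.5 = 13.5 points at r = 0.5 and 84.1 − 79.2 = 4.9 at r = 0.7. Against the 28-df contrast it adds 10.4 and 2.0. At r = 0.9 it adds nothing.

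**Braced T1, with T2/T3 also braced and an immediate constant effect.** Here v = (1, 1, 1). The main effect is undiluted (62.5/54.8/48.7%). Σ(v − mean v)² = 0, so λ = 0 and the interaction rejects at 5%: the effect has dropped out of it.

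**Effect only at T3, v = (0, 0, 1).** Interaction 48.6/71.6/99.5%; adjusted T2/T3 mean 24.2/31.7/66.1%; T3 adjusted for T1 (residual variance 1 − r², same factor, 13 df) 53.7/70.1/98.2%.

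**No true effect.** In simulation (40,000 trials per cell) each test alone rejects in 4.8% to 5.1%. Main effect or interaction, whichever is significant: 9.7% to 9.8%. For independent tests, 1 − 0.95² = 9.75%.

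**The case against.** **The T1 row may mean one condition.** No row in the table lists delivery of the braces, and screening only books the casting. The row could therefore mean outcomes without orthoses plus provision of the first set. Two measured conditions is the more natural reading, but the single-condition reading is open. On it there is no choice of T1 value, and the braced-T1 result falls away. The main-effect dilution and the missing deciding effect remain.

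**Braced T2/T3 is an assumption.** All three testing visits are allotted 120 minutes, which fits one condition throughout, or both at every visit, at least as well as two at T1 and one later. This is fair. The vanishing interaction belongs to one branch only.

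**A G1 v G2 comparison is planned, and its ordinary reading is the group effect.** If that is meant, the deciding effect is the one diluted by an unbraced T1. Nor does the plan permit either effect to count as success. The 10% is conditional on a choice made after the data are seen, which the wording leaves possible.

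**T1 is already a session, so the interaction uses it.** This stands: lack of adjustment for own T1 costs efficiency, not validity. The other measures in the covariate plan could also bring in a baseline walking value, though not each outcome's own.

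**The T2/T3 mean can do worse than the planned interaction.** It does if the effect appears only at T3, and section 13 does expect some longer-term gains.

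**Conclusion.** The point holds as a gap that should be closed. As written, no hypothesis has a defined deciding test, and the main effect gives two thirds of a constant post-baseline effect when T1 is unbraced. The power figures rest on the assumed SD, effect and correlations and show direction and rough size only.

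A reader might infer more, and the documents do not support it:
- *That the ANOVA is invalid.* Each test holds its level. The roughly 10% per outcome arises only if either effect may be chosen afterwards.
- *That two T1 values certainly exist and one will be picked.* If so, and the choice came after the data, simulation gives 11% to 13%. This needs the two-condition reading and depends on an assumed correlation between the two values, so it is not part of the finding.
- *That the braced-T1 problem reaches Hypothesis 3.* It concerns the performance tests only. PDQ-39 has no meaningful braced/unbraced pair at one visit. Steps are taken before the visit: "Steps per day recorded from a pedometer the patients will wear for the week prior to each testing visit". For falls, section 3 mentions only a home log, with no T1 value or window.

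**What to change.** In section 14:
- Define baseline in both groups as the T1 value without orthoses.
- State the brace condition of the T2/T3 performance measurements that enter the test, so that it is clear whether the effect while worn or a carry-over effect is estimated.
- Replace the three-condition sentence with one pre-named test for each outcome that serves a hypothesis: G1 minus G2 over T2 and T3, adjusted for that outcome's unbraced T1 value. Fit it by ANCOVA of the T2/T3 mean or, if sessions are missing, by the mixed model the plan already names.
- For outcomes expected to change late, name T3 adjusted for T1 instead, in advance.
- For falls, first define a baseline window, or omit the adjustment.
- Keep the ANOVA effects, including the interaction, as supportive.
- If braced T1 data are collected, report braced minus unbraced within G1 as a separate paired estimate of the immediate effect.

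In section 4, reword the T1 row so that it has one meaning.

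The cost is SAP wording, a decision on the T2/T3 test condition, and one degree of freedom for the covariate. On either reading of the T1 row the unbraced value is already collected. The real downside is a late effect: if it appears only at T3 and the T2/T3 mean was named, power is 24/32/66% against 49/72/>99% for the interaction. The choice between T2/T3 and T3 should therefore be made deliberately for each outcome.
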